## **TEMPO-1. Statistical Analysis Plan v1.2**

The TEMPO-1 study is a safety in dose-escalation and feasibility trial designed to assess the safety and feasibility of enrolling patients with minor stroke and proven arterial occlusion, and then treating them with low-dose thrombolytic TNK-tPA.

The design is a prospective, observation cohort study. Two sequential cohorts will be treated with TNK-tPA at separate doses. Since all patients will be treated. The relevant outcomes are simply proportions and distributions.

Enrolment in the study is only compatible with drug treatment. Because treatment is a single bolus injection of study drug, all treated patients will be in the analysis cohort for both safety and efficacy.

There is no randomization. The study is open-label with blinded outcome adjudication. The patient is considered enrolled in the trial as soon as drug is administered.

Missing data will be minimized if at all possible. Outcomes will be retrieved on all patients with active and determined follow-up. If a subject is missing one of the outcomes, he will be excluded from the determination of the proportions. No outcome data will be imputed.

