### **Analysis Plan - Outcomes**

#### **1. Safety.**

Proportion of patients with serious adverse safety events.

-all events

-related to study drug (possibly / probably / definite)

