## **1. Feasibility**

Rate of patient enrolment in time. The denominator will be the actual number of days when the study is open to enrolment.

Reporting will be with standard descriptive statistics. All proportions will be reported with exact confidence limits.

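### Does the SAP answer a dose-escalation safety question with one rate pooled over two doses?

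*SAP*

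**What the plan says.** The opening section of the SAP gives the purpose and the structure: "The TEMPO-1 study is a safety in dose-escalation and feasibility trial", and "Two sequential cohorts will be treated with TNK-tPA at separate doses". The summaries follow directly: "The relevant outcomes are simply proportions and distributions". The analysis population is then set in one sentence, which gives the single bolus as its reason: "all treated patients will be in the analysis cohort for both safety and efficacy". The same section states "There is no randomization".

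Under Safety, the headline outcome is "Proportion of patients with serious adverse safety events". The lists under Primary Events and under Secondary and Efficacy Events define further outcomes without mentioning dose. The closing reporting paragraph, under Feasibility, adds descriptive statistics and this rule: "All proportions will be reported with exact confidence limits".

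The SAP gives no cohort size, expected event rate, confidence level or test. It nowhere says that results are shown by dose, compared between doses or combined across doses.

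**The concern.** Dose is the one factor that the design varies, yet the text names a single analysis cohort and gives no outcome by dose. Someone applying that literally could put all treated patients in one denominator and attach an exact binomial interval to the total. Such an interval assumes the same event probability at both doses, which is what an escalation study is meant to examine.

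The stakes would be real. The primary events include symptomatic intracranial hemorrhage and major extracranial hemorrhage. For events like these in a small study, the upper confidence limit is the result that matters most. A pooled limit would be too low for the riskier dose, and a signal at one dose would be diluted by patients who received the other.

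**Working it through.** **Step 1: what the text commits to.** Four statements in the opening section and the reporting rule bear on the point.

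- Structure: two cohorts at different doses. The SAP itself treats the doses as distinct units.
- Summaries: proportions and distributions, stated just after the two cohorts are introduced. Proportions per cohort are at least as natural a reading as one overall proportion.
- Population: everyone treated, for safety and efficacy alike. The reason given is the single bolus. With no partial course of treatment, there is no call for separate safety and efficacy sets. This is a rule about inclusion, not about table columns.
- Precision: exact limits for every proportion. This applies equally to a proportion within one dose cohort.

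None of these requires pooling, and all are met by a table with one column per dose.

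**Step 2: what pooling would cost if it were done.** The SAP has no figure to reproduce, so this is an illustration on assumed inputs: equal cohorts of n = 10, 25 or 50, 0 events at the first dose, and two-sided 95% limits. The exact (Clopper-Pearson) limits for x events in n patients are

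- lower = Beta quantile(0.025; x, n − x + 1), or 0 if x = 0
- upper = Beta quantile(0.975; x + 1, n − x)

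For x = 0 the upper limit reduces to 1 − 0.025^(1/n). At n = 25 this is 13.7%; at n = 50 it is 7.1%.

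| Per dose | Events (dose 1, dose 2) | Dose 1 | Dose 2 | Pooled |
|---|---|---|---|---|
| 10 | 0, 0 | 0% (0–30.8) | 0% (0–30.8) | 0% (0–16.8) |
| 10 | 0, 2 | 0% (0–30.8) | 20% (2.5–55.6) | 10% (1.2–31.7) |
| 25 | 0, 0 | 0% (0–13.7) | 0% (0–13.7) | 0% (0–7.1) |
| 25 | 0, 2 | 0% (0–13.7) | 8% (1.0–26.0) | 4% (0.5–13.7) |
| 25 | 0, 3 | 0% (0–13.7) | 12% (2.5–31.2) | 6% (1.3–16.5) |
| 50 | 0, 0 | 0% (0–7.1) | 0% (0–7.1) | 0% (0–3.6) |
| 50 | 0, 2 | 0% (0–7.1) | 4% (0.5–13.7) | 2% (0.2–7.0) |

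With 2 events, the ratio of the pooled upper limit to that of the dose with events is 31.7/55.6 = 0.57, 13.7/26.0 = 0.53 and 7.0/13.7 = 0.51. The point estimate is halved by construction, because the cohorts are equal and one has no events. The table shows the effect of pooling; it is not evidence that the plan pools.

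**Step 3: whether a between-dose comparison is missing.** The cohorts are sequential and not randomized, so any contrast mixes dose with calendar time and case mix. It would also be imprecise. For 0/25 versus 3/25, the two-sided Fisher p-value is 2 × C(25,3)/C(50,3) = 2 × 2300/19600 = 0.235.

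For assumed true rates of 2% and 10%, let the difference be Δ = 0.08 and the mean rate p̄ = 0.06. The normal-approximation power at a two-sided 5% level is

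Φ{[Δ − 1.96·√(2p̄(1 − p̄)/n)] / √[(0.02·0.98 + 0.10·0.90)/n]}

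This gives 11% at n = 10, 22% at n = 25 and 39% at n = 50. The approximation is rough at these sizes, but a formal contrast would plainly settle little.

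**The case for a change.** The strongest case for a change is that the SAP itself takes on the analysis cohort, the denominators and the reporting of proportions, so the gap cannot simply be passed to the protocol. It settles these matters without naming dose. The study is also open-label, so the choice between pooled and by-dose figures could be made once events by dose are known. The remedy would cost one sentence and some extra table columns.

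Part of this stands. The SAP does leave the layout unstated, and a sentence saying that each proportion is given by dose cohort, with any pooled figure secondary, would be harmless and tidy.

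The rest does not carry far. The document sets no test, success threshold or decision that turns on a pooled rate, so there is little for a late choice to exploit. The two dose cohorts are the design's own units, and a report that withheld counts by dose would fail the study's stated purpose on its face. Once those counts are shown, the pooled figure follows by addition and can mislead no one. Simple proportions with exact limits are not a fault either, since a by-dose report would use the same method.

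**Conclusion.** The concern does not hold as a fault in the analysis. The SAP does not plan a pooled safety rate; the sentence that suggests one defines inclusion and gives the single bolus as its reason. What remains is an unstated reporting detail, which competent analysts would fill by tabulating each dose cohort with its own exact limits. That is fully consistent with the plan as written. A between-dose difference is a matter of preference and would be descriptive at most.

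If someone did report only pooled figures, the loss would be substantial: an upper limit of roughly half that of the dose with the events, over an assumed 10 to 50 patients per dose. Those figures rest on assumed equal cohorts, assumed event counts and an assumed 95% level, none of which the SAP gives. The protocol was not at hand, so the view rests on the SAP's own text. No change to the plan is called for.

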### **Analysis Plan - Outcomes**

#### **1. Safety.**

Proportion of patients with serious adverse safety events.

-all events

-related to study drug (possibly / probably / definite)

#### **Primary Events**

- (i) Symptomatic intracranial hemorrhage defined as new intracranial hemorrhage (ICH, SAH, IVH, SDH) associated with clinical evidence of neurological worsening, in which, the hemorrhage is judged to be the most important cause of the neurological worsening. Clinical worsening will be guided by the NIHSS score of a minimum of 2 or more points different from baseline. Baseline NIHSS score is defined as the time immediately prior (within 10 minutes) to drug administration.
- (ii) Major extracranial hemorrhage defined as life threatening, resulting in hemodynamic compromise or hypovolemic shock, requiring inotropic support or other means to maintain cardiac output, requiring blood transfusion of more than 2 units of packed red blood cells, or associated with a fall in hemoglobin greater than or equal to 5 g/L.

- (iii) Life-threatening angioedema defined as severe airway obstruction requiring intubation.
- (iv) Life-threatening thrombolysis associated hypotension defined as a drop in blood pressure that requires inotropic support.

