### **Secondary and Efficacy Events**

- (i) Asymptomatic or minor or moderate bleeding—defined as requiring a transfusion of 2 units of packed red blood cells or less, not severe as defined above, or associated with a fall in hemoglobin of less than 5 g/L; minor—defined as bleeding not requiring transfusion, not causing hemodynamic compromise, usually including hematoma, subcutaneous bleeding, oozing from puncture sites, and may require modification of drug regimen; and asymptomatic—defined as bleeding that results in no symptoms.
- (ii) Complete neurological and functional recovery at 30 days defined as:  
NIHSS 0 and mRS 0 and absence of all neurological symptoms and signs
- (i) Complete neurological and functional recovery at 90 days defined as:
  - a. NIHSS 0-1 and mRS 0-1 and Barthel Index > 90 AND
  - b. Absence of all neurological symptoms and signs AND
  - c. Complete lifestyle recovery such that the patient is back to all prior activities; specifically, this includes driving a car, working and/or active leisure activities.
- (ii) Proportion of patients with any recurrent stroke event (stroke or TIA) within 90 days.
- (iii) Recanalization defined on follow-up 4-8 hour CTA.
- (iv) Proportion of patients with observable infarction on follow-up imaging.
- (v) Volume of infarction.
- (vi) Recurrent stroke or progression of stroke with any persistent functional neurological worsening at 24 hours after enrolment.
- (vii) Recurrent stroke or progression of stroke with any persistent functional neurological worsening with NIHSS score 4 or more points greater than at enrolment

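### A hemoglobin fall of 5 g/L alone makes an extracranial bleed a primary major event, a cut out of scale with the criteria beside it and overlapping the minor and asymptomatic tiers

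*SAP*

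**What the plan says.** Under Analysis Plan - Outcomes, the SAP names four primary safety events. The second, Primary Events item (ii), is a major bleed outside the skull. Its criteria are alternatives:

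- the patient's state: danger to life, circulatory compromise or shock, or a need for inotropes or similar support
- the amount of blood given, worded as "requiring blood transfusion of more than 2 units of packed red blood cells"
- last in the list, a laboratory criterion, worded as "or associated with a fall in hemoglobin greater than or equal to 5 g/L"

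The first item of Secondary and Efficacy Events covers the lesser bleeds in three clauses:

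- The first clause (moderate, by elimination) sets a transfusion limit, "requiring a transfusion of 2 units of packed red blood cells or less, not severe as defined above". Its alternative is a laboratory limit, "associated with a fall in hemoglobin of less than 5 g/L".
- The minor clause describes "bleeding not requiring transfusion, not causing hemodynamic compromise, usually including hematoma, subcutaneous bleeding, oozing from puncture sites".
- The asymptomatic clause describes "bleeding that results in no symptoms".

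Outcome adjudication is blinded, and proportions are reported with exact confidence limits. The SAP states no sample size.

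**The concern.** The major-bleed criteria are alternatives, so the hemoglobin criterion decides on its own. The other criteria describe a patient in danger or one needing at least three whole units of red cells. A fall of 0.5 g/dL is a different order of severity and is small enough to arise from measurement and ordinary variation.

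The lower tiers do not correct this. The exclusion of severe bleeds is written only in the first clause, and it uses the word severe although the tier above is called major. The minor and asymptomatic clauses carry neither an exclusion nor a hemoglobin limit, so one bleed can belong to two or three tiers.

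The stake is the safety result. Major extracranial hemorrhage is a primary event in a study whose purpose is safety across two dose cohorts. Blinded adjudication does not help, because a blinded adjudicator applies the same written cut.

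**Working it through.** The SAP gives no figure to reproduce. Four checks follow. The definitions come from the SAP; every other input is an assumption and is marked so.

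**1. Unit.** 5 g/L ÷ 10 = 0.5 g/dL. Against an assumed baseline of 100–150 g/L this is 5/150 = 3.3% to 5/100 = 5.0%. The same numeral in g/dL would be 50 g/L, ten times larger.

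**2. Scale against the transfusion criterion.** Let r be the hemoglobin equivalent of one red-cell unit (assumed). The central range is 8–12 g/L, and 5 and 15 g/L are shown as wide limits.

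| r (g/L per unit) | 5 g/L in units (5/r) | 2 units (2r) | 2r/5 | 3 units (3r) | 3r/5 |
|---|---|---|---|---|---|
| 5 | 1.00 | 10 g/L | 2.0 | 15 g/L | 3.0 |
| 8 | 0.63 | 16 g/L | 3.2 | 24 g/L | 4.8 |
| 12 | 0.42 | 24 g/L | 4.8 | 36 g/L | 7.2 |
| 15 | 0.33 | 30 g/L | 6.0 | 45 g/L | 9.0 |

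Comparing with exactly 2 units is the conservative choice, since the criterion requires more than 2. Even so, the two cuts would agree only if a unit were worth 5/2 = 2.5 g/L. The direction of the mismatch holds over the whole range.

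**3. Tiers applied as written.**

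| Bleed | Major | First (moderate) clause | Minor | Asymptomatic |
|---|---|---|---|---|
| Puncture-site ooze, no transfusion, 6 g/L fall | yes | no | yes | no |
| Symptom-free bleed, no transfusion, 6 g/L fall | yes | no | yes | yes |
| 2 units transfused, 20 g/L fall | yes, on hemoglobin | meets the transfusion limit | no | no |
| Puncture-site ooze, no transfusion, 4 g/L fall | no | yes | yes | no |

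The first two rows need no numerical assumption beyond the example itself. In the third row, if severe is read as major, the exclusion removes the bleed from the lower tier. A bleed needing 1–2 units then stays there only when its fall is under 5 g/L. That tier is narrow but not logically empty.

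**4. Chance variation.** With no true change and a normally distributed paired difference, P(fall ≥ c) = 1 − Φ(c/SD). The SDs are assumed.

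| SD of difference | c = 5 g/L | c = 16 g/L | c = 24 g/L |
|---|---|---|---|
| 3 g/L | 4.8% | under 0.01% | under 0.01% |
| 5 g/L | 15.9% | 0.07% | under 0.01% |
| 7 g/L | 23.8% | 1.1% | 0.03% |
| 10 g/L | 30.9% | 5.5% | 0.8% |

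These are per bleed with paired hemoglobin values, not per enrolled patient. For chance alone they are a ceiling, because the fall must also be judged associated with the bleed.

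**Effect on a proportion.** One reclassified patient with no other counted event adds 1/n: 1/20 = 5 percentage points, 1/50 = 2 percentage points (n assumed).

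**The case against.** **The tiers were meant to be exclusive.** On hemoglobin the two definitions are exact complements, at or above 5 g/L against below it. The secondary item is a single outcome evidently meant for bleeds that are not major. If the exclusion is read across all three clauses, the overlap disappears. That reading is open, but the position of the phrase and the word severe do not secure it. It also leaves the main problem in place: the 6 g/L ooze would then simply be major. It is true that the overlap itself does not inflate the primary count; the low cut does.

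**The numbers are assumed.** The SAP gives no conversion from units to hemoglobin, no SD and no n. Transfusion is a response to bleeding, not a measure of the fall. A chance fall is by construction not caused by the bleed, and adjudicators may reject it. This stands as a limit on size: the expected number of misclassified patients cannot be stated. It does not reverse the direction.

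**A unit slip is unproven.** The SAP writes g/L in both places. A slip for g/dL is the likely explanation, but a wrong number, or an intended one, cannot be ruled out from this document.

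**The consequence is limited.** The SAP has no hypothesis test, no escalation or stopping rule tied to this event, and no stated composite of the four events. The safety heading speaks of serious events, so a trivial ooze might never be reported there, and any error overcounts harm. These points are fair, but the SAP does not make seriousness a condition of the major-bleed definition. An overcount still distorts the safety proportion of each dose cohort.

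**Conclusion.** The concern holds and the definition must be fixed. Two parts rest on the wording alone: a fall of 5 g/L associated with an extracranial bleed is sufficient for a primary major event, and the minor and asymptomatic clauses do not exclude such a bleed. The mismatch of scale is also clear from the text. Its size depends on an assumed 8–12 g/L per unit, which puts 2 units at 3.2–4.8 times the hemoglobin cut; at 5–15 g/L per unit the multiple is 2–6.

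The effect on the reported result cannot be estimated from the SAP. Its direction is upward, and in small cohorts one patient is enough to matter. Confidence is high that the text is wrong as written, and lower on the reason for the error.

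**What to change.** Before any event is adjudicated:

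1. Verify the unit and value of the hemoglobin cut against the definition the sponsor intended. The choice of threshold remains with the sponsor.
2. Correct Primary Events item (ii) and the first item of Secondary and Efficacy Events together. If g/dL was intended, write 5 g/dL (50 g/L) in both. If g/L was intended, justify it against the other major criteria.
3. In the secondary item, refer to major rather than severe bleeds, and apply the exclusion to the minor and asymptomatic clauses as well.
4. State that each bleed is assigned to the single highest tier it meets.

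The cost is SAP wording only. No new data are needed, because the present rule already requires the hemoglobin values.

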### **Secondary and Efficacy Events**

- (i) Asymptomatic or minor or moderate bleeding—defined as requiring a transfusion of 2 units of packed red blood cells or less, not severe as defined above, or associated with a fall in hemoglobin of less than 5 g/L; minor—defined as bleeding not requiring transfusion, not causing hemodynamic compromise, usually including hematoma, subcutaneous bleeding, oozing from puncture sites, and may require modification of drug regimen; and asymptomatic—defined as bleeding that results in no symptoms.
- (ii) Complete neurological and functional recovery at 30 days defined as:  
NIHSS 0 and mRS 0 and absence of all neurological symptoms and signs
- (i) Complete neurological and functional recovery at 90 days defined as:
  - a. NIHSS 0-1 and mRS 0-1 and Barthel Index > 90 AND
  - b. Absence of all neurological symptoms and signs AND
  - c. Complete lifestyle recovery such that the patient is back to all prior activities; specifically, this includes driving a car, working and/or active leisure activities.
- (ii) Proportion of patients with any recurrent stroke event (stroke or TIA) within 90 days.
- (iii) Recanalization defined on follow-up 4-8 hour CTA.
- (iv) Proportion of patients with observable infarction on follow-up imaging.
- (v) Volume of infarction.
- (vi) Recurrent stroke or progression of stroke with any persistent functional neurological worsening at 24 hours after enrolment.
- (vii) Recurrent stroke or progression of stroke with any persistent functional neurological worsening with NIHSS score 4 or more points greater than at enrolment

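### The missing-outcome rule can drop known non-recoveries, above all deaths, from the denominator of complete recovery at 30 and 90 days

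*SAP*

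**What the plan says.** Under Secondary and Efficacy Events the SAP defines complete recovery twice, each time with every component joined by 'and'.

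- At 30 days: "NIHSS 0 and mRS 0 and absence of all neurological symptoms and signs".
- At 90 days there are three parts. Part (a) sets limits on three scales: "NIHSS 0-1 and mRS 0-1 and Barthel Index > 90 AND". Part (b) asks that the patient be free of any neurological symptom or sign. Part (c) asks for a return to ordinary life, worded as "Complete lifestyle recovery such that the patient is back to all prior activities".

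The introductory section sets one missing-data rule for all outcomes: "If a subject is missing one of the outcomes, he will be excluded from the determination of the proportions. No outcome data will be imputed". The same section says that "all treated patients will be in the analysis cohort for both safety and efficacy", and that follow-up will be pursued so as to keep missing data to a minimum. The closing section on feasibility and reporting promises exact confidence limits for every proportion.

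Nowhere does the SAP say how a death before the visit is scored for recovery. Nor does it say whether an observed failing component settles the composite when another component is unobserved.

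**The concern.** With an all-components endpoint, one failure decides the answer: the patient has not recovered, whatever the other components would have shown. An exclusion rule that turns on missingness ignores this. It can remove patients whose result is known, and every such patient is a failure.

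Death is the clearest case. A patient who dies before the 30- or 90-day visit cannot have an NIHSS or Barthel Index measured there, and no effort at follow-up will supply them. Under the rule as written, an analyst may treat the outcome as missing and drop the patient. That is hard to square with keeping all treated patients in the efficacy cohort.

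The second case depends on how the rule is read. If an outcome means a component, a survivor with an observed mRS of 3 and no NIHSS examination is also dropped, although failure is already certain.

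At stake are the reported recovery proportion, its exact limits, and reproducibility: two analysts following this SAP could obtain different rates from the same data.

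**Working it through.** **Inputs.** The SAP supplies the all-components definitions, the exclusion rule and the exact-limits method. It gives no cohort size, recovery rate, death rate or loss rate, so there is no stated figure to reproduce. The values of n, x and k below are assumptions for illustration, and the 95% level for the limits is also assumed.

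**Step 1: who is affected under each reading of the rule.**

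| Patient | 'Outcome' = whole composite | 'Outcome' = each component |
|---|---|---|
| Died before the visit | Kept only if death is scored as failure, which the SAP does not state | Dropped |
| Survivor, one component failed, another missing | Can be kept as not recovered | Dropped |
| Survivor, observed components good, one missing | Undetermined, dropped | Undetermined, dropped |

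**Step 2: effect of dropping known failures.** Let x be the number of recoveries among n treated patients, and k the number of known non-recoveries dropped.

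- Known failures counted: x/n.
- Known failures dropped: x/(n-k).
- Ratio: n/(n-k), which is above 1 whenever k > 0 and x > 0.

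The numerator is the same in both, because a known failure is never a recovery.

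| Assumed n, x | k = 0 | k = 1 | k = 2 |
|---|---|---|---|
| 20, 12 | 12/20 = 60.0% | 12/19 = 63.2% | 12/18 = 66.7% |
| 25, 15 | 15/25 = 60.0% | 15/24 = 62.5% | 15/23 = 65.2% |
| 25, 10 | 10/25 = 40.0% | 10/24 = 41.7% | 10/23 = 43.5% |
| 50, 30 | 30/50 = 60.0% | 30/49 = 61.2% | 30/48 = 62.5% |

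**Step 3: exact limits (Clopper-Pearson, 95%) for n = 25, x = 15.**

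- k = 0: 60.0% (38.7 to 78.9)
- k = 1: 62.5% (40.6 to 81.2)
- k = 2: 65.2% (42.7 to 83.6)

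Counting known failures as not recovered gives the k = 0 line however many of the failures are deaths or have incomplete data.

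**Step 4: undetermined patients.** Suppose 15 of 25 are observed recoveries and 2 of the 25 have only good observed components with one missing. Dropping them gives 15/23 = 65.2%. If neither in truth recovered, the rate is 15/25 = 60.0%; if one did, 16/25 = 64.0%; if both did, 17/25 = 68.0%. The reported figure can be too high or too low, so no direction can be claimed for this group.

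**The case against.** The strongest reply is that the listed outcome is complete recovery, and that NIHSS, mRS and Barthel are criteria inside its definition. On that reading a survivor with mRS 3 and no NIHSS has a determined outcome and stays in. This stands. A reader might infer that such survivors are lost on any reading of the rule, but the text does not support that.

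On death, it can be said that a patient who has died is plainly not back to prior activities, so 90-day failure follows from component (c), and that scoring of deaths may be left to the protocol. This stands in part. Component (c) gives an analyst a route to the right answer at 90 days, but the 30-day definition has no such component. And the SAP is not silent on missing data: it states a rule that, followed literally, permits the exclusion. A convention of giving death the worst mRS score may be in mind, but the SAP does not adopt it, and the no-imputation sentence could be read as barring assigned scores.

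That sentence is not itself an obstacle, though. Classifying a patient from death or from an observed failing component uses known facts and imputes nothing.

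The size is also open to challenge. With 10 failures among 25, k = 2 means that a fifth of all failures are dropped, and no passage supports that or any other count. A shift of 5.2 points sits inside an interval about 40 points wide.

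Two further inferences are tempting. One is that the bias always favours treatment; Step 4 shows that this holds only for known failures. The other is that a more harmful dose would come out looking better. The SAP plans no formal comparison of doses and attaches no decision rule to recovery, and serious events are reported separately under Safety. It also does not say that losses follow a bad course, plausible as that is.

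**Conclusion.** The concern holds in a limited form. The exclusion rule is badly matched to an all-components endpoint. It permits deaths before the visit to leave the recovery denominator and, if outcomes are read as components, survivors already known to have failed as well. For these known failures the reported rate can only rise, by the factor n/(n-k), provided there is at least one recovery.

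The size cannot be taken from the SAP. For the assumed cohorts of 20 to 50 patients with 40% or 60% recovery, one or two dropped failures add from 1.2 points (30/50 to 30/49) to 6.7 points (12/20 to 12/18) in the cases tabulated. With none dropped the effect is zero.

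The consequence is confined to a secondary descriptive proportion and its exact limits in a non-randomised study; no test depends on it. The correction is worth making because the ambiguity is real and removing it costs almost nothing.

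**What to change.** Add to both the 30-day and the 90-day recovery definitions: a patient who has died by the visit, or who fails any observed component, is counted as not recovered and remains in the denominator; only a patient whose composite is still undetermined, with no failing component observed and at least one component unobserved, is treated as missing. Report the number excluded as undetermined for each dose cohort beside the proportion and its exact limits.

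This relies on observed facts alone, leaves the no-imputation rule intact, and brings the denominator closer to the all-treated cohort that the SAP promises. The cost is a sentence of wording and a count in the report, with no new data to collect. The recovery proportion may come out slightly less favourable.
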